Other information to be collected include date of birth, gender, ethnicity, height, weight, duration of condition, and type and dosage of medication.

Data Analysis/Statistical Analysis

For each of the primary and secondary measures, we will perform a Shapiro-Wilk test for normality to assess the assumption of normality. If the outcome variable is approximately normally distributed, a paired t-test will be used to statistically compare outcome metrics before and after the intervention within a condition. If the normality assumption is not met, the Wilcoxon signed rank test will be used as an alternative to the paired t-test for this statistical comparison. Bonferroni multiple hypothesis correction will be utilized for a corrected significance level.

To compare across conditions, an analysis of variance (ANOVA) test will be performed if the outcome variable is normally distributed. If the normality assumption is not met, the Kruskal Wallis test will be used as the non-parametric version of ANOVA. We may also employ a repeated measures ANOVA test for inclusion of all three timepoints.

Organizational Relationships

CIONIC works closely with Edge Analytics, a consulting firm who has been contracting for CIONIC for over two years. The firm is primarily responsible for algorithm development and statistical analyses of kinematic and EMG data. [name], [name], and [name] are employees of Edge Analytics who have been working closely with Cionic. [name] is a sub-investigator on this study.

Risk & Benefit Assessment

The Cionic Neural Sleeve has been tested extensively in previous studies. Across these prior studies, the Cionic Neural Sleeve has been evaluated for walking and exercise mode, approved for FDA 510k submission and its intended use in a simulated home environment, and for home usability with no adverse events.

However, any study of this kind comes with some known risks, that although rare, are associated with participation:

- Discomfort from the electrical stimulation
- Minor skin irritation at the sites of sensor/electrode pad placement
- Muscle fatigue from prolonged device use
- Anxiousness due to the anticipation of receiving an electrical stimulation
- Injury caused by unintended falls while using the Cionic Neural Sleeve
- Exposure to coronavirus disease 2019 (COVID-19) or other communicable disease

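### The Shapiro-Wilk rule checks the outcome where the paired t-test needs the differences, can mix means with ranks across outcomes, and leaves both between-arm tests without baseline adjustment

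*Combined protocol and SAP*

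**What the plan says.** The combined protocol and SAP, section Data Analysis/Statistical Analysis, sets one rule for all measures: "For each of the primary and secondary measures, we will perform a Shapiro-Wilk test for normality to assess the assumption of normality".

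- **Within arm.** "If the outcome variable is approximately normally distributed, a paired t-test will be used to statistically compare outcome metrics before and after the intervention". Otherwise "the Wilcoxon signed rank test will be used as an alternative to the paired t-test".
- **Between arms.** "an analysis of variance (ANOVA) test will be performed if the outcome variable is normally distributed". Otherwise "the Kruskal Wallis test will be used as the non-parametric version of ANOVA".
- **All visits.** "We may also employ a repeated measures ANOVA test for inclusion of all three timepoints". This is optional and has no rank counterpart.

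The section gives no significance level for the normality check. It does not say whether the check is pooled or by arm, which visit it uses, or whether the between-arm tests take final or change scores. It names no baseline covariate. Table 2 schedules every primary outcome at baseline, midpoint and end of study, so the baseline values will exist.

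**The concern.** The paired t-test assumes that within-person differences are approximately normal, and ANOVA assumes the same of residuals within arms. The section names neither. Skewed scores can have normal differences, and roughly normal scores can have skewed differences. The rule can therefore drop the t-test without cause, or keep it when the differences are clearly non-normal.

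The rule also lets the data decide, outcome by outcome, whether means or ranks are compared. The protocol's benchmarks are on the mean scale: 14.48 for WOMAC-PF, 8.74 for WOMAC-Pain and 0.12 m/s for gait speed. A Kruskal-Wallis result gives no mean difference to set against them.

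A separate matter affects precision. Neither ANOVA nor Kruskal-Wallis, as described, adjusts for the baseline score, and a three-arm trial of 45 has little precision to spare.

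**Working it through.** **Inputs from the documents.** Three arms and about 45 participants (Overview of Study); two-sided 5% (Participation Selection and Randomization); effect size 0.71 for WOMAC function (Appendix A).

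**Assumptions.** 15 per arm; normality check at 5%; baseline-to-final correlation ρ of 0.5 or 0.7; no Bonferroni division, because the number of tests is not given. The documents give no distribution or correlation for any outcome. Simulations used 3,000 to 5,000 runs per setting.

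**1. The plan's own figure.** For 0.71, the two-group size is 2(1.960 + 0.842)² / 0.71² = 31.1, rounded up to 32 per group (t-based 32.1). The paired t-test solution is 17.6, so 18. Both match Appendix A, so the planning rests on mean-scale t-tests. Only the effect size is used below.

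**2. Within-arm check, skewed scores and normal differences.** Score = √ρ × person effect + √(1 − ρ) × normal error, with ρ = 0.7. The person effect is a standardised gamma or log-normal variable. Shapiro-Wilk rejection rates:

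| Person effect | n | Final score | Difference |
|---|---|---|---|
| Normal | 15 | 5.0% | 4.4% |
| Gamma, shape 8 (mild skew) | 15 | 7.6% | 5.6% |
| Gamma, shape 2 | 15 | 14.4% | 4.6% |
| Log-normal, log-SD 0.5 | 15 | 17.3% | 5.3% |
| Gamma, shape 2 | 45 | 42.1% | 4.8% |
| Log-normal, log-SD 0.5 | 45 | 42.8% | 4.9% |

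The n = 45 rows apply if the check pools the arms.

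**3. The reverse case.** With a normal baseline and exponential-type changes at n = 15, the differences fail in 68% of runs and the final score in 8%. In 61% of runs the score passes while the differences fail. At n = 45 that last figure is 81%.

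**4. Between-arm check.** If the check is done within each arm, the outcome and the one-way ANOVA residual differ only by a constant, so Shapiro-Wilk gives the same answer. If it is pooled over 45, with normal data and both stimulated arms shifted by 0.71 SD, it rejects in 5.1% (raw) against 5.0% (residual). With skewed data the rates are 20% against 22% and 36% against 43%. A large gap needs a very large shift in one arm: at 3 SD, 43% against 4%.

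**5. What the rule does to error and power.** Type I error of the rule was 4.3–5.3% in every setting. Power with 3 × 15 and both stimulated arms 0.71 SD better:

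| Person effect, ρ | Final: ANOVA | Final: by the rule | Change: ANOVA | Change: by the rule | Baseline-adjusted |
|---|---|---|---|---|---|
| Normal, 0.5 | 46.8% | 46.5% | 47.7% | 47.7% | 59.1% |
| Normal, 0.7 | 48.1% | 47.9% | 72.2% | 72.0% | 77.0% |
| Skewed, 0.5 | 48.8% | 49.2% | 47.5% | 47.0% | 59.3% |
| Skewed, 0.7 | 49.1% | 50.8% | 71.9% | 71.2% | 78.3% |

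Against plain ANOVA on the same score, the rule moves power by −0.7 to +1.7 points. Within an arm of 15 (skewed scores, ρ = 0.7), the paired t-test has 73.0%, the signed rank test 70.3% and the rule 72.4%.

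**6. Analytic check of the baseline gain.** The between-arm sum of squares is 15 × [(0.473)² + 2 × (0.237)²] = 5.04 in units of the outcome variance. Dividing by the error variance gives the noncentrality:

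- Final score, error variance 1: 5.04, power 48%.
- Change score, 2(1 − ρ): 5.04 at ρ = 0.5, power 48%; 8.40 at 0.7, power 71%.
- Baseline-adjusted, 1 − ρ²: 6.72 at 0.5, power 60%; 9.88 at 0.7, power 78%.

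These agree with the simulation. Over all simulation settings, the rule on final scores ranged over 45–52%.

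**The case against.** The strongest reply is that the section is ambiguous rather than wrong. It says "we will perform a Shapiro-Wilk test for normality to assess the assumption of normality", which could mean the assumption of whichever test is being considered, and the outcome variable could be the change. For ANOVA checked within arms, raw outcome and residual are equivalent. These points stand for the between-arm test. For the paired test, the sentence applies the condition to the outcome and then compares values before and after, so the measure itself is the natural reading. On either reading the rule cannot be reproduced without more detail.

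A reader might infer that the rule often pushes the trial onto rank tests that discard the baseline, and that this causes the power loss. The documents do not support that:

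- The Wilcoxon signed rank test ranks differences from baseline, so it uses the baseline as the paired t-test does. Kruskal-Wallis takes no covariate, but the planned one-way ANOVA has none either, and both could be run on change scores.
- How often the rule switches depends on distributions that are not given. At 15 per arm it was a minority event in the settings above. Even so, eight independent, perfectly normal measures would give 1 − 0.95⁸ = 34% chance of at least one switch.
- A working treatment makes the pooled outcome a mixture of arms, but at 0.71 SD the effect on the check is negligible.
- The section sets the check by measure. It does not state that it is repeated by visit.

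The optional repeated measures ANOVA would include baseline, but it is not a commitment.

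**Conclusion.** The point holds in limited form and merits a change, though it does not threaten validity. For the within-arm comparison, the rule as naturally read checks the wrong quantity and can err in both directions; the rates depend on the assumed distributions. For the between-arm comparison, the rule leaves type I error near 5% and moves power by at most about 2 points. Its cost there is that the quantity compared may differ between outcomes while the benchmarks are on the mean scale.

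The larger gain comes from baseline adjustment, not from removing the check. Compared with final scores, it is worth roughly 10 points of power at ρ = 0.5 and nearly 30 at 0.7. Compared with change scores, it is about 12 and 5 to 7 points. These figures assume 15 per arm with no dropout, both stimulated arms 0.71 SD better, and unadjusted 5%. A Bonferroni division or dropout would lower all of them.

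**What to change.** In Data Analysis/Statistical Analysis:

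1. Delete the Shapiro-Wilk rule.
2. For each continuous outcome measured at baseline, prespecify one model: 12-week value by arm, adjusted for the baseline value. Report arm differences with confidence intervals.
3. Check the residuals by plot.
4. Run the rank test as a fixed sensitivity analysis for every outcome, whatever the plots show.
5. Report within-arm changes as means with confidence intervals.
6. Give adherence its own unadjusted comparison, since it has no baseline value.

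If the missing baseline adjustment is also raised as its own point, handle the two together and count the power gain once. The cost is SAP wording and a little programming, with no extra participants, visits or data.

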A sample size of 32 participants was calculated to be sufficient for a two-tailed significance level of 5% and a power of 80% (Appendix A). This was adjusted to 45 participants with knee osteoarthritis to allow for dropouts. Recruitment for this study will be conducted using a recruitment flyer and through the CIONIC website. Recruitment will be based on a first come

basis. Interested participants will complete a questionnaire to be reviewed according to the inclusion and exclusion criteria. Responses will then be reviewed, and prospective participants will be invited to schedule a virtual meeting with a study staff member who will screen the prospective subject for an understanding of the study and for their voluntary participation. All participants will be assigned a unique number using a computer random number generator and randomly assigned to a group by a researcher. All participants will receive their assigned intervention at their first lab visit.

Inclusion Criteria

- Persons with knee osteoarthritis between the ages of 22 and 75
- Ability to walk a duration of 30 minutes per walking session (with or without an assistive device), for three days per week
- Able to tolerate the device for up to 1 hour per lab session
- No recent change in medication or exacerbation of symptoms over the last 60 days
- Radiographic KOA K&L grade 2 or 3 or physician diagnosed mild or moderate KOA if radiographic imaging is not available
- No hyaluronic acid or cortisone injection into knees in previous 12 months

Exclusion Criteria

- Lower motor neuron disease or injury (e.g. peripheral neuropathy) that may impair response to stimulation
- Absent sensation in the impacted or more impacted leg

- Inadequate response to stimulation, as defined as inability to achieve muscle contraction or tolerate stimulation
- Inability to ambulate with the sleeve in place of an ankle foot orthosis (AFO)/knee ankle foot orthosis (KAFO) if utilized
- Use of FES devices in the past year
- Demand-type cardiac pacemaker or defibrillator
- Malignant tumor in the impacted or more impacted leg
- Existing thrombosis in the impacted or more impacted leg
- Fracture or dislocation in the impacted or more impacted leg that could be adversely affected by motion from stimulation
- History of knee surgery
- History of other types of arthritis
- History of neurological disease
- History of seizures or diagnosed with epilepsy/seizures
- Current pregnancy

Methodology

Overview of Study

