This study is a randomized controlled trial. Figure 2 depicts a flow diagram of the study design. Participants will be screened for eligibility through a questionnaire, and after study details are explained and consent is obtained, they will be invited to the study site. Assessments will be conducted at CIONIC Inc., and involve approximately 45 patients for a 12 week study period.

CIONIC

CIONC FOR ORTHOPEDICS

All subjects will be assigned an electrical stimulation system to wear on the most impacted leg and be prescribed a home-based exercise and walking program. Subjects will be randomly assigned into three groups: (a) control; (b) NMES+; (c) NMES+FES. The control group will not receive stimulation for the exercise and walking program, whereas subjects in NMES+ will receive stimulation during exercises, and subjects in the NMES+FES group will receive stimulation during exercises and walking. Outcome measures will be assessed at baseline, 6 weeks after baseline, and end of study (Table 2). Equipment and additional feedback will be collected at the end of study. These three groups will be analyzed using several outcome measures. Primary outcome measures of the study are quadriceps strength, perceived functional capacity, self-reported pain, and walking performance. Secondary interest will be adherence to program, thigh muscle volume, functional ability of the lower limb, and quality of life. The CIONIC system will be used to track adherence (duration of sessions, frequency of use).

[figure not shown]

Figure 2: Study flow

Table 2: Study overview

Comparison Groups	Treatment Schedule	Timing and Outcome Measures
Control (unstimulated exercise and walking)	Exercise: 5x/week for 12 weeks Progression every 3 weeks	At baseline, midpoint and end of study: Quadriceps strength Perceived functional capacity Self-reported pain Walking performance Thigh muscle volume Functional ability of lower limb Quality of life EMG activity
NMES+ (NMES+exercise and unstimulated walking)	Walking: 10 min, 3x/week for 12 weeks Progression up to 30 min by end of study	Weekly: Adherence to program
NMES+FES (NMES+exercise and FES+walking)		

Participant Identification, Recruitment & Informed Consent

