Appendix A: Power Analysis

Power and Significance Level

[figure not shown]
These are set to standard,

Power = 0.8

Significance Level (alpha) = 0.05

Metric	Effect Size used in calculation	Required sample size when comparing participants' sessions (paired sample)	Required sample size when comparing group A to group B
WOMAC - Function bivariate	0.71 ²⁷	18	32
WOMAC - Pain bivariate	0.41 ²⁷	49	94
WOMAC - Function Standing/Walking bivariate	0.45 ²⁷	41	78

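### The Bonferroni correction sits with the within-arm before-after tests, and no family or divisor is given for the between-arm tests on four co-equal primary outcomes; the stated power assumes an uncorrected 0.05

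*Combined protocol and SAP*

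**What the plan says.** Under *Data Analysis/Statistical Analysis*, the first paragraph covers all primary and secondary measures. It sets out a normality check and then a paired t-test or Wilcoxon signed rank test within each condition. It ends: "Bonferroni multiple hypothesis correction will be utilized for a corrected significance level". The second paragraph begins: "To compare across conditions, an analysis of variance (ANOVA) test will be performed if the outcome variable is normally distributed". It gives Kruskal-Wallis as the non-parametric alternative and allows an optional repeated measures ANOVA over the three timepoints. It mentions no correction and names no contrast to follow a significant omnibus result.

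*Overview of Study* states: "Primary outcome measures of the study are quadriceps strength, perceived functional capacity, self-reported pain, and walking performance". No order or hierarchy is given. *Walking Performance* then splits the last outcome into gait speed, averaged separately for comfortable and fast walking, and six-minute walk distance.

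On sample size, *Participation Selection and Randomization* calls 32 participants "sufficient for a two-tailed significance level of 5% and a power of 80" per cent, and adds: "This was adjusted to 45 participants with knee osteoarthritis to allow for dropouts". *Appendix A* sets "Significance Level (alpha) = 0.05" and has the rows "WOMAC - Function bivariate 0.71 ²⁷ 18 32" and "WOMAC - Pain bivariate 0.41 ²⁷ 49 94". The last two figures in each row are the paired and the two-group requirement.

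**The concern.** The randomised question is the comparison between arms. Objective 1 and the hypotheses are framed as stimulated groups against the unstimulated group, and Aim 2 looks to the randomised design for statistically significant evidence. The before-after tests within an arm do not use the randomisation. Yet the only multiplicity control in the plan is written next to those tests.

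The plan can be read in two ways, and each leaves a gap.

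- **Correction confined to the within-arm tests.** Several co-equal primary outcomes are then tested between arms at 0.05 each, with nothing limiting the overall chance of a false positive.
- **Correction meant for the arm tests too.** The divisor is then unknown, and the sample size was computed at a level that those tests will not use.

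In both cases the family could be chosen after the results are seen. An omnibus test also does not say which stimulated arm differs from control, so further tests will follow whose level is not set.

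**Working it through.** **Inputs.** Two-sided alpha 0.05, power 0.80 and effect size 0.71 (*Appendix A*); three arms and four primary outcomes (*Overview of Study*); six measures after the split under *Walking Performance*; 45 enrolled (*Participation Selection and Randomization*). The allocation ratio is not stated; I assume 1:1:1, so 45/3 = 15 per arm.

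**1. Reproduce the plan's figure.** Two-sample, normal approximation: n per arm = 2(1.960 + 0.842)²/0.71² = 31.1, rounded up to 32. The noncentral-t solution is 32.1, and power at 32 per arm is 79.8%. The 0.41 row gives 94 in the same way. So 32 is a per-arm number at uncorrected two-sided 0.05. No multiplicity adjustment is built in.

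**2. Arm tests uncorrected, no true effect.** For m independent tests, P(at least one rejection) = 1 − 0.95^m.

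- m = 4: 1 − 0.8145 = 18.5%
- m = 6: 1 − 0.7351 = 26.5%

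The outcomes will be correlated, by an amount the documents do not give. I simulated three-arm ANOVAs with 15 per arm, six equicorrelated outcomes and 20,000 runs:

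| Correlation | Any significant omnibus test | Significant omnibus test and a stimulated arm significantly better than control |
|---|---|---|
| 0 | 26% | 12% |
| 0.3 | 24–25% | 11% |
| 0.5 | 21–22% | 9% |
| 0.7 | 17% | 7% |

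The ranges reflect differences between repeat runs. The last column is the figure relevant to a false claim of benefit.

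**3. Arm tests corrected.** Two-sample t power, effect size 0.71, noncentrality 0.71·√(n/2), which is 1.94 at n = 15 and 2.84 at n = 32:

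| Level | 15 per arm | 32 per arm |
|---|---|---|
| 0.05 | 47% | 80% |
| 0.05/4 = 0.0125 | 25% | 61% |
| 0.05/6 = 0.00833 | 21% | 55% |

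For 80% power, about 46 per arm are needed at 0.05/4 and 50 at 0.05/6.

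The planned test is a three-group ANOVA, so I checked that as well, with 45 in total and the extreme means 0.71 apart. With the third mean midway, power is 37% at 0.05 and 15% at 0.05/6. With the third mean equal to the lower one, it is 48% and 22%. The two-sample figures are therefore a fair guide.

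**4. Which follow-up rule holds the family at 5%.** Suppose each omnibus test uses 0.05/6 and, where it passes, each stimulated arm is compared with control at the same 0.05/6. With three arms, a false rejection within one outcome then has probability at most 0.05/6. If all three means are equal, the omnibus test protects. If only one pair is equal, there is only one true pairwise null. Over six outcomes the bound is 6 × 0.05/6 = 5%.

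If instead the pairs are tested at each outcome's Holm level, that level rises from 0.05/6 towards 0.05. With NMES+ equal to control and NMES+FES strongly effective on six independent outcomes, simulation gave 8–9% for at least one false NMES+ claim.

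**The case against.** Four points on the other side carry weight.

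- **Scope is inferred.** The section opens by addressing every primary and secondary measure, and the Bonferroni sentence names no test. It may be meant for everything. The paragraph break suggests otherwise but does not settle it. What is certain is that scope, family and divisor are unstated.
- **No familywise rate is stated.** A reader might infer that a stated property is wrong under either reading. The documents do not support that. The 5% is never labelled familywise, so if the arm tests are uncorrected, each still runs at the stated level. The fault under that reading is uncontrolled multiplicity, not a contradiction.
- **No success rule is stated.** The hypothesis lists its outcomes jointly. If success required all of them, there would be no inflation from picking any one. But the plan does not say so, and it tests each outcome separately. A reader might also take 26% as the chance of a false claim of benefit. It is not: it includes omnibus rejections where control does better or only the stimulated arms differ.
- **Counts depend on the reading.** *Overview of Study* lists four outcomes; six is my count from the later sections. Counting both follow-up visits would give twelve tests (46% if independent), but the plan does not specify a separate ANOVA at each visit, so I do not rely on that.

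**Conclusion.** The point stands as a gap in multiplicity control of the randomised comparisons. As the text is laid out, the arm tests are uncorrected. The chance of at least one false-positive omnibus test is then 19% for four and 26% for six independent outcomes, falling to about 17% for six at correlation 0.7. The chance of a false claim of benefit is smaller, 7% to 12% for six measures, and still above 5%.

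If the correction is meant to reach the arm tests, the 80% power does not apply to them. At 15 per arm, correction takes two-sample power from 47% to 25% or 21%; at 32 per arm it would go from 80% to 61% or 55%.

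A reader might attribute the whole fall from 80% to 21% to the correction. That would be wrong. The part from 80% to 47% arises because a per-arm 32 is used as a total, which is a separate error and would remain at an uncorrected 0.05.

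These figures assume equal allocation, no dropout from the 15 per arm, normal outcomes and the correlations shown.

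**What to change.** In *Data Analysis/Statistical Analysis*:

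- Define the primary family as six between-arm tests at 12 weeks: quadriceps strength, WOMAC physical function, WOMAC pain, comfortable gait speed, fast gait speed and six-minute walk distance. For the three walking measures, name in advance which stimulation condition is analysed; otherwise the count exceeds six.
- Test each omnibus hypothesis at 0.05/6 = 0.00833. Where it passes, compare each stimulated arm with control at the same fixed 0.05/6, not at rising Holm levels.
- Label the 6-week tests and all within-arm before-after tests as descriptive.

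In *Participation Selection and Randomization* and *Appendix A*, restate the power at the corrected level and for the number per arm that is actually planned.

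This changes wording only and needs no new data or procedures. The cost is that the stated power becomes visibly less favourable: about 21% for a pairwise comparison at 15 per arm and effect size 0.71.

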Acknowledging the benefits of combined electrotherapy and KOA as a progressive and degenerative condition with unlikely regression or restoration of damaged structures, the study aims to investigate the effects of stimulation assisted activities to delay the disease progression and muscle atrophy in those with KOA. Thus, the purpose of this research is to investigate if stimulation assisted (NMES and FES) activities can combat disuse atrophy for individuals diagnosed with KOA. This study will use a home-based medical device (Cionic Neural Sleeve NS-100, K213622, CIONIC, San Francisco, CA) to administer electrical stimulation and measure its effect on outcomes that include quadriceps strength, perceived functional capacity, pain, and walking performance.

Significance

Adults with KOA spend most of their day engaging in sedentary behavior and report worse physical function⁸, which may lead to progression of the condition, increased functional dependence and decreased quality of life²². Existing literature shows that NMES assisted exercise may counter disuse atrophy in sedentary individuals²³, but because there has been minimal research investigating the effects of FES in the KOA community, exploration of this study is warranted.

Figure 1: Cionic Neural Sleeve system

Note: Left: Cionic Neural Sleeve showing the configuration of the FES and electromyographic (EMG) electrode arrays. Center: Cionic mobile application interface for setting FES parameters (frequency, pulse width, intensity) and current field steering. Right: Cionic Neural Sleeve on body.

Research Objectives

1. Analyze the effects of electrical stimulation assisted interventions versus a conventional exercise program on muscle strength, perceived function, and pain in KOA.
2. Compare the effects of unassisted walking and stimulation assisted walking on walking performance in KOA.
3. Measure the compliance of electrical stimulation assisted interventions to a conventional exercise program on the effects of pain and perceived function in KOA.

Hypotheses

It was hypothesized that combined electrotherapy groups will show larger muscle mass and strength improvements; improved gait kinematics, pain and perceived function; and a high compliance to the assigned program compared to the unstimulated group.

Specific Aims

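### The only committed between-group test is a three-arm omnibus test with no stated baseline adjustment and no stimulation-versus-control contrast; a baseline-adjusted week-12 model with two named contrasts would address Objective 1 at little cost

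*Combined protocol and SAP*

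**What the plan says.** **Question.** Under Research Objectives, Objective 1 is: "Analyze the effects of electrical stimulation assisted interventions versus a conventional exercise program on muscle strength, perceived function, and pain in KOA". Under Hypotheses: "It was hypothesized that combined electrotherapy groups will show larger muscle mass and strength improvements", with the unstimulated group as comparator. Both are comparisons of stimulation with control.

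**Design.** Overview of Study: "Subjects will be randomly assigned into three groups: (a) control; (b) NMES+; (c) NMES+FES". The allocation ratio is not stated. All outcomes except adherence are measured at baseline, week 6 and week 12. The exercise and walking prescriptions are the same in every arm.

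**Analysis.** Data Analysis/Statistical Analysis contains:
- within a condition, "a paired t-test will be used to statistically compare outcome metrics before and after the intervention within a condition", or the Wilcoxon signed rank test;
- "Bonferroni multiple hypothesis correction will be utilized for a corrected significance level", which closes the within-condition paragraph and gives neither family nor divisor;
- "To compare across conditions, an analysis of variance (ANOVA) test will be performed if the outcome variable is normally distributed", otherwise Kruskal-Wallis;
- "We may also employ a repeated measures ANOVA test for inclusion of all three timepoints", which is optional and does not say which model term is to be read.

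**Sample size.** Appendix A has one column for paired comparisons and one for a two-group comparison (group A against group B). Neither is a three-arm test. Of the sample of 32, the text says: "This was adjusted to 45 participants with knee osteoarthritis to allow for dropouts".

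**The concern.** An omnibus test over three arms rejects the statement that all arms are equal. It does not say which arm differs or whether the difference favours stimulation. With no follow-up contrast named, the plan can reach significance and still leave Objective 1 open. The follow-up choices (which pairs, week-12 value or change, which alpha) could then be made after the results are seen.

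Baseline is measured in everyone, but the plan does not state that the committed test uses it.

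The before/after tests cannot fill the gap. Every arm does the same exercise and walking programme, and the Benefits section itself expects routine exercise to help with or without stimulation. A change within a stimulated arm therefore mixes the programme with the stimulation. The plan does not label these tests descriptive.

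The word *condition* adds to the uncertainty. In the analysis section it seems to mean randomised arm; under Walking Performance it means stimulation on or off.

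**Working it through.** **Inputs.** From the documents: effect size 0.71 for WOMAC function, two-sided 5%, power 80% (Appendix A); 45 enrolled; three arms. Assumed: 1:1:1 allocation, so 15 per arm; correlation ρ between baseline and week 12 of 0.3, 0.5, 0.7 or 0.8 (none is given).

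**1. The plan's own figure.** Two groups, normal approximation: n = 2(1.960 + 0.842)²/0.71² = 31.1, so 32 per group (t-test solution: 32.13). Appendix A's 32 is thus the size of *each group* in a pairwise comparison that the analysis section does not contain. The paired entry of 18 also reproduces (paired t-test: 17.59), but only if 0.71 is in units of the SD of the paired differences. The same 0.71 is therefore used in two different units.

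**2. Committed omnibus test, week-12 value.** Noncentrality = 15 × (2/3) × 0.71² = 5.04; F with 2 and 42 df gives 48% power. The result is the same for true means (0, 0, 0.71), (0, 0.71, 0.71) and (0, −0.71, −0.71), so the p-value cannot tell one effective arm from two, or benefit from harm. On change from baseline (variance 2(1−ρ)), power is 36/48/71/88% for ρ = 0.3/0.5/0.7/0.8.

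**3. One stimulation-versus-control contrast.** Noncentral t with noncentrality (0.71/s)·√(15/2) and error pooled over three arms. Here s² = 1 for endpoint only (42 df), 2(1−ρ) for change (42 df) and 1−ρ² for ANCOVA (41 df). Example at ρ = 0.5: endpoint 0.71 × 2.739 = 1.944, power 47.6%; ANCOVA 1.944/√0.75 = 2.245, power 59.2%. With 0.71 in week-12 SD units and alpha 0.05:

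| ρ | Endpoint | Change | ANCOVA | Gain over better alternative (points) |
|---|---|---|---|---|
| 0.3 | 47.6% | 36.2% | 51.2% | 3.6 |
| 0.5 | 47.6% | 47.6% | 59.2% | 11.6 |
| 0.7 | 47.6% | 68.9% | 75.8% | 6.9 |
| 0.8 | 47.6% | 85.2% | 88.6% | 3.4 |

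With 32 completers (11 v 11 in the contrast), endpoint-only gives 36% and ANCOVA 39/46/61.5/76%.

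**4. The other unit.** If 0.71 is in SD-of-change units, the difference in week-12 SDs is 0.71 × √(2(1−ρ)) = 0.84/0.71/0.55/0.45. ANCOVA power becomes 65/59/54/52%, so the trend with ρ reverses. The gain over the better alternative stays at about 4 to 12 points.

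**5. Cost of multiplicity.** ANCOVA power per contrast:

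| Alpha | Unit of 0.71 | ρ = 0.3 | 0.5 | 0.7 | 0.8 |
|---|---|---|---|---|---|
| 0.025 (two contrasts) | week-12 SD | 39.5% | 47.4% | 65.5% | 81.6% |
| 0.025 | SD of change | 54% | 47% | 42% | 40% |
| 0.05/8 (two contrasts × four outcomes, assumed) | week-12 SD | 22% | 28% | 45% | 64% |

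**6. Choice of procedure.** Chance of finding at least one stimulation-versus-control effect with ANCOVA, by simulation (100,000 trials, week-12 SD units, ρ as above). Omnibus then pairwise: 44/52/70.5/86% if one arm works, 50.5/59/77/90% if both do. Two contrasts at 0.025: 40/48/65/81% and 54/62/80/91%. Both procedures hold the false-positive rate below 5% when the arms do not differ (4.1 to 4.6%).

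**The case against.** **The analysed form is open, so the test need not ignore baseline.** This stands. The hypothesis speaks of larger improvements, which leans towards change, and a change score uses baseline. A reader might infer that the plan is committed to an unadjusted week-12 comparison. The text does not establish that; it only names no covariate and fixes no form.

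**The bare omnibus test can be the more powerful one.** This also stands. In week-12 SD units at ρ = 0.7 and 0.8, the omnibus test on change (71% and 88%) exceeds two ANCOVA contrasts at 0.025 when one arm works (65% and 81%). It names no arm, however, so the two powers are not for the same conclusion.

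**The optional repeated-measures ANOVA would do nearly as well.** Partly. Read on the arm-by-visit term for one pair, with the effect already present at week 6 and compound symmetry, it gives 37/49/72/89%, close to ANCOVA at high correlation. But it is optional and the term is not named.

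**Bonferroni may be meant to cover follow-up comparisons.** Possible, but the sentence sits with the paired tests, and no follow-up comparisons are listed.

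**The within-arm tests are not offered as efficacy evidence.** Correct. A reader might infer that the plan rests its case on them, but the documents do not say so. The request is only that they be labelled.

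**For walking, the change is more than wording.** This stands. Under Lab Visits and Walking Performance, participants assigned to stimulation walk first without and then with it, at visits that include the initial one. An ANCOVA must therefore say which walk is the baseline and which is the outcome.

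**Conclusion.** The point holds as an inexpensive improvement. The plan has a valid randomised test, but that test does not by itself say whether either stimulation arm differs from control, and no committed analysis does.

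The gain from baseline adjustment, about 3 to 12 points of power for one contrast, holds under either unit of the 0.71. It rests on 15 per arm, equal allocation and correlations of 0.3 to 0.8. The absolute power levels are not robust: at alpha 0.05, ANCOVA runs from 51% to 89% if 0.71 is in week-12 SDs, and from 65% down to 52% if it is in SDs of change.

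A reader might infer that the revised analysis would *answer* Objective 1. The figures do not support that. With alpha split over two contrasts, per-contrast power reaches 80% only at 0.71 week-12 SDs, a correlation near 0.8 and no dropout, and it falls further if the correction also covers several primary outcomes. The change directs the analysis at the right question; it does not repair the sample size.

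**What to change.** 1. For each primary outcome, make the main analysis an ANCOVA of the week-12 value on randomised arm and baseline, or a mixed model with baseline, arm, visit and arm-by-visit from which the week-12 arm effect is read.
2. Report NMES+FES versus control and NMES+ versus control with confidence intervals.
3. State one familywise procedure: the omnibus test followed by pairwise tests (valid for three arms), or Bonferroni or Holm over the two contrasts. Say whether it also covers the several primary outcomes.
4. Give a counterpart for the Kruskal-Wallis branch, such as rank ANCOVA or pairwise rank tests under the same procedure.
5. For walking outcomes, use the unstimulated baseline walk as covariate, because a stimulated baseline depends on assignment. State whether the unstimulated or the stimulated week-12 walk is analysed.
6. Label the within-arm tests descriptive, and write *randomised arm* where that is what *condition* means.

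**Cost.** A few sentences and one degree of freedom for baseline; no new visits or data. The real trade-off is the alpha split shown above. Omnibus-then-pairwise finds an effect more often if only one arm works, and two contrasts at 0.025 more often if both do, so the choice should be made and written down before the data are seen.
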